**France**

Inclusion and exclusion criteria required in France are included in the *Clinical Investigation Plan Addendum: France – Addendum for France to Clinical Investigational Plan Document Number 10234430DOC*.

**3.3.6 Informed Consent**

Prior to enrolling in the trial, patients should be fully informed of the details of trial participation as required by applicable regulations, the site's IRB and by Medtronic. Informed consent must be obtained from each patient prior to conducting any protocol-induced activities beyond standard of care, by using the informed consent form (ICF) approved by that site's IRB and by Medtronic. The ICF must be signed and dated by the patient and by the person obtaining the consent. Any additional persons required by the site's IRB to sign the informed consent form must also comply.

Prior to the patient signing the ICF, the investigator or authorized designee will fully explain to the patient the nature of the research, trial procedures, anticipated benefits, and potential risks of participation in the trial. The investigator or delegate will allow adequate time for the patient to read and review the consent form and to ask questions. Signing the ICF serves to document the written and verbal information that the investigator or authorized delegate provides to the patient, the patient's understanding of the information, and his/her agreement to participate. The investigator or authorized delegate must document in the patient's medical records that the patient was consented and the date on which the consent was obtained. The original signed consent form will be retained in the patient's trial records and a copy of the informed consent will be provided to the patient.

**3.3.7 Revisions in Patient Information and Informed Consent Form**

Medtronic will inform the investigators whenever information becomes available that may be relevant to the subject's continued participation in the trial. The revised information will be sent to the investigator for

---

iiFor subjects with a patent LIMA undergoing transaxillary (subclavian) access, the minimal access vessel mean diameter is 5.5 mm for the Evolut 23R, 26R, and 29R TAV, and 6.0 mm for the Evolut 34R and Evolut PRO TAV.

approval by the IRB/EC. After approval by the IRB/EC, a copy of this information must be provided to the participating subjects, and the informed consent process as described above needs to be repeated. The investigator or his/her designee should inform the subject in a timely manner.

### 3.3.8 Screening, Enrollment, and Randomization

The process of patient screening, subject enrollment, and randomization is as follows (Figure 1):

1. Patients identified by or presented to the trial site with aortic stenosis will be screened by the investigative team for the criteria described in 3.3.5, Subject Selection Criteria, using available medical records, including relevant imaging studies previously performed for diagnostic purposes.
2. If the patient is deemed a potential candidate for the trial, the investigational status of the Medtronic TAVR System and all aspects of the trial will be explained to the patient. The patient will then be invited to participate in the Low Risk Trial. Sites participating in the LTI Sub-study will also invite patients to consent for the LTI Sub-Study.
3. If the patient agrees to participate, written informed consent will be obtained. This will be considered the point of enrollment, and the subject will be assigned a Subject ID number.
4. The subject will undergo transthoracic echocardiography (TTE) to assess his/her degree of aortic stenosis.
5. Subjects who meet the criteria for aortic stenosisiii will undergo:
  - a. Multi-Detector Computed Tomography (MDCT) of their peripheral vasculature and aortic annulus to assess anatomic suitability for the Medtronic TAVR, and
  - b. Local Heart Team assessment to determine his/her operative risk profile for SAVR.
6. If the local Heart Team considers the subject anatomically suitable for implantation and at low risk for SAVR, the subject's clinical information will be submitted to the Screening Committee. The Heart Team assessment must be documented. The following information should be submitted to the Screening Committee:
  - Clinical assessments including STS-PROM, medical history and co-morbidities
  - TTE data on degree of aortic stenosis
  - MDCT data on anatomical suitabilityiv
7. The Screening Committee will review the clinical information to confirm the eligibility of the subject for implantation.
8. Subjects confirmed eligible for implantation by the Screening Committee will be randomized in a 1:1 fashion to either TAVR or SAVR, stratified by site and the need for coronary revascularization during SAVR. Coronary artery bypass graft (CABG) should be conducted during the index procedure. Concomitant percutaneous coronary intervention (PCI)v and TAVR is encouraged; however staging is left to the discretion of the operator. Intervention/repair of the mitral and/or tricuspid valve is only

---

iiiIf a subject has balloon aortic valvuloplasty after their qualifying TTE, they must have repeat TTE to confirm he/she meets criteria for severe aortic stenosis as described in Section 3.3.5.1 prior to submission to the screening committee.

[figure not shown]
iv Anatomical suitability will be confirmed by Medtronic Screening Lab. Information on MDCT procedures and sizing recommendations is provided in Appendix II, Section 4.0.

v Index PCI should be performed at the TAVR implanting center; index PCI operators will be considered investigators.

allowed if deemed necessary during the SAVR procedure, but there must be no intent to do this type of intervention/repair prior to implant.

9. Trial randomization will not be blinded. Once randomization is complete and a treatment arm is assigned, crossover from SAVR to TAVR treatment is not permitted. The sponsor will strictly monitor device dispensation to ensure that only those subjects randomized to the Medtronic TAVR treatment arm receive the Medtronic TAV. Distribution of the subjects within the trial groups will be controlled at the implanting sites by means of central randomization using interactive voice/web randomization service (IXRS). The randomization scheme will be securely stored at the IXRS provider.
10. Implantation should occur within 90 days of Screening Committee approval.
11. Subjects who consent to participate in the LTI study will also follow the LTI sub-study protocol as described in APPENDIX VII: LEAFLET THICKENING/IMMOBILITY SUB-STUDY PROTOCOL

***Patients should give written consent before undergoing any protocol-required testing. However, if any of protocol-required baseline/screening evaluations (eg, echocardiography, MDCT, coronary arteriography, lab work) have been performed for clinical diagnostic purposes prior to consenting, they can be used as the protocol-required exams, provided they were obtained within the protocol-required time windows and contain the necessary information.***

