### 3.3.5.2 Exclusion Criteria

If any of the following exclusion criteria are present, the prospective subject is not eligible for implantation:

1. Any condition considered a contraindication for placement of a bioprosthetic valve (eg, subject is indicated for mechanical prosthetic valve).
2. A known hypersensitivity or contraindication to any of the following that cannot be adequately pre-medicated:
  - a. aspirin or heparin (HIT/HITTS) and bivalirudin
  - b. ticlopidine and clopidogrel
  - c. Nitinol (titanium or nickel)
  - d. contrast media
3. Blood dyscrasias as defined: leukopenia (WBC <1000 mm^3), thrombocytopenia (platelet count <50,000 cells/mm^3), history of bleeding diathesis or coagulopathy, or hypercoagulable states.
4. Ongoing sepsis, including active endocarditis.
5. Any percutaneous coronary or peripheral interventional procedure with a bare metal stent within 30 days prior to randomization, or drug eluting stent performed within 180 days prior to randomization.
6. Multivessel coronary artery disease with a Syntax score >22 and/or unprotected left main coronary artery.
7. Symptomatic carotid or vertebral artery disease or successful treatment of carotid stenosis within 10 weeks of Heart Team assessment.
8. Cardiogenic shock manifested by low cardiac output, vasopressor dependence, or mechanical hemodynamic support.
9. Recent (within 2 months of Heart Team assessment) cerebrovascular accident (CVA) or transient ischemic attack (TIA).
10. Gastrointestinal (GI) bleeding that would preclude anticoagulation.
11. Subject refuses a blood transfusion.
12. Severe dementia (resulting in either inability to provide informed consent for the trial/procedure, prevents independent lifestyle outside of a chronic care facility, or will fundamentally complicate rehabilitation from the procedure or compliance with follow-up visits).
13. Estimated life expectancy of less than 24 months due to associated non-cardiac co-morbid conditions.
14. Other medical, social, or psychological conditions that in the opinion of the investigator precludes the subject from appropriate consent or adherence to the protocol required follow-up exams.
15. Currently participating in an investigational drug or another device trial (excluding registries).
16. Evidence of an acute myocardial infarction ≤30 days before the trial procedure due to unstable coronary artery disease (WHO criteria).
17. Need for emergency surgery for any reason.

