**3.3.11 Subject Disposition**

Sites will maintain a log of subjects consented, his/her assigned treatment group, date attempted and implanted, as well as the Subject ID numbers assigned to each patient. Subjects who are consented but are not taken to the procedure room for implantation will be exited from the trial, and will not be followed beyond the date of trial exit.

Subjects who are taken to the procedure room for implantation but do not receive a TAV or surgical valve for any reason will be followed for the trial duration. Subjects that have their TAV or SAVR bioprosthesis explanted will be followed for the trial duration.

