#### 6.2.2. Randomized Population

If the subject signs informed consent, meets all inclusion and none of the exclusion criteria, and the Heart Team determines the subject is suitable for randomization in the trial, then the subject is reviewed by the Screening Committee. If the subject is approved by the Screening Committee and the subject is randomized to either TAVR or SAVR, the subject is added to the randomized population. Within the randomized population the following analysis sets are distinguished:

- **The intention to treat (ITT) set:** Subjects are reported according to the randomized assignment, SAVR or TAVR, regardless of what, if any, therapy was actually received. Time zero begins at the date of randomization.
- **The as treated (AT) set:** The AT set consists of all ITT subjects with an attempted implant procedure, defined as when the subject is brought into the procedure room and any of the following have occurred: anesthesia administered, vascular line placed, TEE placed or any monitoring line placed. Subjects will be analyzed according to their first attempted procedure (TAVR or SAVR). Time zero begins at the date of the first TAVR or SAVR attempted procedure.
- **The implanted set:** The Implanted set consists of all the AT subjects who are actually implanted with either the Transcatheter Aortic Valve (TAV) or Surgical Aortic Valve (SAV). Time zero begins at the date of the first TAVR or SAVR attempted procedure.
- **The per protocol (PP) set:** The PP set is defined based on the International Council for Harmonisation (ICH) E9 Statistical Principles, which will consist of the following:
  1. All implanted subjects who were implanted according to their randomization; and
  2. Subjects without early exit (eg., lost of follow up) before 24 months (730 days), except those experiencing the primary endpoint (death or disabling stroke) prior to the early exit; and

This document is electronically controlled. Printed copies are considered uncontrolled.

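### Endpoint events at an index PCI staged before TAVR fall outside the as-treated analyses, while endpoint events from CABG done at the index operation are counted.

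*Protocol*

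**What the plan says.** Protocol 3.3.8 (item 8) stratifies randomisation by the need for coronary revascularisation and treats the two arms differently:

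- SAVR arm: "Coronary artery bypass graft (CABG) should be conducted during the index procedure".
- TAVR arm: concomitant PCI "and TAVR is encouraged; however staging is left to the discretion of the operator". Nothing requires a staged PCI to follow TAVR. A footnote calls it the index PCI, asks that it be done at the implanting centre, and treats its operators as investigators.

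Exclusion 5 (Protocol 3.3.5.2) looks back from randomisation only: a bare metal stent within 30 days, or a "drug eluting stent performed within 180 days prior to randomization". Item 10 of 3.3.8 adds: "Implantation should occur within 90 days of Screening Committee approval".

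SAP 6.2.2 states: "The AT set consists of all ITT subjects with an attempted implant procedure". Subjects are grouped by the first attempted valve procedure, and "Time zero begins at the date of the first TAVR or SAVR attempted procedure". For the ITT set, "Time zero begins at the date of randomization". Protocol 3.3.3.2.2 and SAP 6.2.2 and 6.6 make AT the main set for the primary endpoint and every secondary safety endpoint. SAP 6.6 adds ITT, implanted and per-protocol runs for the primary endpoint only.

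Protocol 3.3.11: "Subjects who are consented but are not taken to the procedure room for implantation will be exited from the trial". Adverse events are recorded from enrolment until exit (Protocol 3.3.26.2).

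**The concern.** In the revascularisation stratum, treating the coronary disease is part of the assigned strategy in both arms. With CABG at the index operation, its endpoint events fall on or after time zero. With PCI staged before TAVR, a stroke, life-threatening bleed, major vascular complication or kidney injury at that PCI falls before time zero. A subject who dies at that PCI never enters the AT set.

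Harm from the same part of the strategy is thus counted under one arrangement and not the other, and the omission makes TAVR look better. More subjects would not remove it. Neither document says how events between a staged PCI and TAVR are to be handled.

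**Working it through.** **1. Can an index PCI fall between randomisation and TAVR?** Yes. Staging is at the operator's discretion, exclusion 5 stops at randomisation, and implantation may follow Screening Committee approval by up to 90 days.

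**2. Where do the events fall?**

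| Procedure | AT analyses | Primary-endpoint ITT run |
|---|---|---|
| CABG at index operation | On or after time zero: counted | Counted |
| PCI with or after TAVR | On or after time zero: counted | Counted |
| PCI before TAVR, TAVR attempted later | Before time zero: not counted | Counted |
| PCI before TAVR, death before any valve attempt | Not in AT set | Death counted |
| PCI before TAVR, survivor with no valve attempt | Not in AT set | Counted up to exit; later follow-up, including the 90-day mRS, may be lost |

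The ITT column does not apply to the 30-day composite, which has no ITT run.

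**3. The plan's own sample size.** Inputs from Protocol 3.3.3.4.3: 15% in each arm, margin 0.06, alpha 0.05 (taken one-sided), power 85%. The Farrington-Manning constrained rates are 0.1848 and 0.1248.

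n per arm = {[1.645 × √(0.1848×0.8152 + 0.1248×0.8752) + 1.036 × √(2×0.15×0.85)] / 0.06}² = [(0.8385 + 0.5234) / 0.06]² = 515.2

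That is 516 per arm, or 1032 in total, as stated. Next, 1032/0.94 = 1098 (stated 1100) and 1100 × 1.09 = 1199 (stated 1200). The present point does not alter these figures.

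**4. Size of the omission.** Events missed in the TAVR arm = r × s × e, where r is the share needing revascularisation, s the share of those with PCI staged before TAVR, and e the endpoint-event rate per such PCI. The documents give none of the three, so all values are assumptions. The product is an upper bound for given inputs, because a subject who also has a counted event after TAVR is not missed. Events are per 600 subjects (1200/2).

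Primary endpoint. The last column is the single-look type I error of the test in step 3 with 516 per arm, SAVR at 15% and a true TAVR rate of 21%, so that the AT analysis sees 21% minus the missed share:

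| r | s | e | Missed, points | Events per 600 | Nominal 5% becomes |
|---|---|---|---|---|---|
| 0.10 | 0.25 | 0.5% | 0.0125 | 0.075 | 5.05% |
| 0.15 | 0.50 | 1% | 0.075 | 0.45 | 5.33% |
| 0.20 | 0.50 | 2% | 0.20 | 1.2 | 5.93% |
| 0.30 | 0.75 | 2% | 0.45 | 2.7 | 7.27% |

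Third row as an example: the observed difference is 0.208 − 0.150 = 0.058. The standard error is 0.02380 under both the constrained null rates (0.2091 and 0.1491) and the observed rates. Then z = (0.060 − 0.058 − 1.645 × 0.02380) / 0.02380 = −1.561, and Φ(−1.561) = 0.0593. This is the frequentist single-look test that guided the sample size, not the three-look Bayesian rule, whose thresholds are not in these documents.

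30-day composite:

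- Low end: 0.10 × 0.25 × 2% = 0.05 points (0.3 events per 600).
- Moderate high end: 0.25 × 0.75 × 5% = 0.94 points (5.6 events).
- Wider high end: 0.30 × 0.75 × 8% = 1.8 points (10.8 events).
- Within the revascularisation stratum (s × e): 0.25 × 2% = 0.5 points to 0.75 × 5% = 3.75 points, or 0.75 × 8% = 6.0 at the wider end.

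**5. Can the gap be seen in the data?** Only in part. The SAVR procedure list (Protocol 3.3.13) records concomitant procedures. The TAVR list (3.3.12) has no item for PCI or its date.

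**The case against.** The strongest reply is that the exposure is narrow and already partly covered. Concomitant PCI is encouraged, staging may also follow TAVR, and exclusion 6 removes complex coronary disease, so the upper assumptions may be high. The primary endpoint has an ITT run from randomisation, and SAP 6.10 plans a treatment-by-revascularisation interaction test. The 30-day composite, where the effect is largest, lies outside the labelling hierarchy (Protocol 3.3.3.7, SAP 6.9). All of this stands and limits the size. It does not give the composite an analysis that counts these events.

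It could also be argued that a PCI meets the AT definition because a vascular line is placed in a procedure room. But the definition concerns an attempted implant, and time zero names only TAVR or SAVR. If PCI is meant, the SAP must say so.

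A reader might infer more than the documents support:

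- *That ITT also loses deaths at the PCI.* It does not: a death after randomisation and before exit is an ITT event.
- *That events are dropped from one arm only.* The AT set drops all events between randomisation and the procedure, including those while waiting for SAVR. The imbalance concerns revascularisation harm.
- *That a PCI complication leading to a surgical valve adds that event to SAVR.* Such a subject would be analysed as SAVR, but the PCI event still precedes time zero and counts in neither arm. Only a new event at or after surgery would count there.
- *That every CABG complication is counted.* The protocol says CABG should be at the index procedure, so this holds only for CABG done then.

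Moving AT time zero to the PCI is a tempting remedy, but it has its own bias. With implantation up to 90 days after approval, TAVR pacemakers could fall outside the 30-day window, implant-anchored visits would no longer line up, and waiting time would count in one arm only.

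**Conclusion.** The point holds for PCI staged before TAVR and for the AT analyses: following the plan as written leaves those endpoint events out, in the direction that favours TAVR. For death or disabling stroke the effect is probably small, about 0.01 to 0.45 points against a 6-point margin, with ITT as partial cover. The documents do not support the inference that it undermines the non-inferiority conclusion. For the 30-day composite it is larger, about 0.05 to 0.94 points and up to 1.8 under the wider assumptions, with no ITT run to set beside it. The direction follows from the text; the sizes rest entirely on assumed revascularisation, staging and event rates. The events are still reported as adverse events, so what is missing is a rule for counting them.

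**What to change.** 1. **Protocol 3.3.11:** keep in follow-up any randomised subject who had an index PCI, even if no valve implant is attempted.
2. **SAP 6.6 and 6.7:** leave AT time zero as it is, including for the pacemaker endpoint and visit windows. Add a prespecified analysis by randomised arm that counts events in both arms from randomisation: through 24 months for the primary endpoint, and through 30 days after the first attempted valve procedure for the composite. A subject with an index PCI and no valve attempt is counted through 30 days after that PCI for the composite. Index-PCI events in subjects randomised to TAVR then count as TAVR. Report overall and by revascularisation stratum. For the primary endpoint this builds on the ITT run already planned. Because Appendix V dates kidney injury from the procedure, state that the index PCI counts as a procedure here.
3. **Protocol 3.3.12:** record the index PCI and its date on the TAVR procedure form, as concomitant procedures already are for SAVR.

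The cost is a few more subjects to follow, one form item, one more analysis and a slightly less favourable TAVR composite. Time from randomisation to valve procedure may differ between arms, so report it alongside. Adverse events are already collected from enrolment. No change to PCI timing is proposed.

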**Notes**

1. TTE, MDCT, coronary arteriography, or labs performed for diagnostic purposes prior to consent may be used for the baseline/screening exams, provided they were performed within window and contain the necessary data.
2. Only the sites participating in the LTI Sub-study will consent for both the main study and LTI Sub-study.
3. Subjects who give consent for LTI Sub-study will follow sub-study protocol in addition to main protocol.

**Figure 1.** Flow diagram of trial entry process.

### 3.3.9 Required Evaluations

Follow-up protocol required evaluations should be performed at the trial site. The protocol required evaluations for each trial interval are listed as follows, and summarized in Table 2 and Table 3.

#### **Baseline/Pre-implant Required prior to Screening Committee Submission (within 12 weeks prior to submission to the Screening Committee; except for MDCT and coronary arteriography) vi**

- Clinical assessment and history (eg, clinical history, STS-PROM, co-morbidities, NYHA) v
- Coronary arteriography
- TTE
- Heart Team assessment
- MDCT (peripheral vasculature and aortic annulus)
- Adverse Events

#### **Baseline/Pre-implant Required prior to Index Procedure**

- 12-lead ECG
- Complete blood count, creatinine,
- Modified Rankin Score
- Kansas City Cardiomyopathy Questionnaire (KCCQ)
- Euro-Qol (EQ-5D) Quality of Life survey
- Anti-thrombotic medications
- Adverse Events

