1F	
 
1. Added Japan regional sponsor address
 
2. Clarified echocardiography inclusion criteria must be at rest
 
3. Added Japan for investigation sites and regions
 
4. Section 2.0 Background was updated with recent information
 
5. Added TAVR Implant Team definition
 
6. Added and enrolled to Screening Population once a patient provides informed consent
 
7. Added Intervention/repair of the mitral and/or tricuspid valve is only allowed during the SAVR procedure, but there must be no intent to perform the intervention/repair prior to the implant
 
8. Separated baseline assessments to clarify which are required prior to screening submission and which are required prior to the index procedure
 
9. Clarified the discharge window
 
10. Clarified that MRS assessment should be performed with any suspected or confirmed stroke event
 
11. Clarified that in countries where required, specifically the United States and Japan, the local heart team's interventional cardiologist(s) and cardiac surgeon(s) must jointly participate in the intra-operative technical aspects of the TAVR procedure
 
	[name]/Sr. Clinical Research Specialist [name]/Clinical Research Specialist

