**Visit Windows**

Baseline	Within 12 weeks prior to submitting to the screening committee (except for MDCT and coronary arteriography) as noted in Section 3.3.9)
Discharge	Discharge from index procedure or 7 days post implant, whichever comes first
30 Days	Between 30 and 45 days post implant
6 Months	Between 183 and 213 days post implant
1 Year	Between 365 and 395 days post implant
18 Months	Between 545 and 575 days post-implant
2 Year	Between 730 and 760 days post-implant
3 – 10 years	Between implant anniversary date and +/-60 days after

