**Confidential**

**Rationale for Delta:** A 5-point improvement or decrease in KCCQ is the minimum difference that is clinically relevant.

5. Transvalvular mean gradient at 1 year (superiority). The hypothesis of interest is

$$H: \mu_{TAVR} < \mu_{SAVR}$$

where  $\mu_{TAVR}$  and  $\mu_{SAVR}$  denote the average mean gradient at 1 year, measured in mmHg. This objective will be evaluated using a Bayesian version of a two-sample t-test. The posterior probability  $P(H | \text{data})$  will be calculated and compared to a threshold of 0.975.

6. Effective orifice area at 1 year (superiority). The hypothesis of interest is

$$H: \mu_{TAVR} > \mu_{SAVR}$$

where  $\mu_{TAVR}$  and  $\mu_{SAVR}$  denote the mean effective orifice area at 1 year, measured in  $\text{cm}^2$ . This objective will be evaluated using a Bayesian version of a two-sample t-test. The posterior probability  $P(H | \text{data})$  will be calculated and compared to a threshold of 0.975.

7. Change in Kansas City Cardiomyopathy Questionnaire (KCCQ) score from baseline to 30 days (superiority). The hypothesis of interest is

$$H: \mu_{TAVR} > \mu_{SAVR}$$

where  $\mu_{TAVR}$  and  $\mu_{SAVR}$  denote the mean changes in the KCCQ score from baseline to 30 days. For subjects with KCCQ score at both baseline and 30 days, the change in KCCQ will be calculated as  $\text{KCCQ}_{30\text{day}} - \text{KCCQ}_{\text{baseline}}$ . The objective will be evaluated using a Bayesian version of a two-sample t-test. The posterior probability  $P(H | \text{data})$  will be calculated and compared to a threshold of 0.975.

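### Baseline KCCQ is due only before the index procedure, so it can be completed after open-label assignment, and two labelling tests use raw change from it

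*Protocol*

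**What the plan says.** Protocol Section 3.3.9 has two baseline lists. The first, "Baseline/Pre-implant Required prior to Screening Committee Submission", contains the clinical assessment with NYHA, echocardiography, CT, coronary arteriography and the Heart Team assessment. The second, "Baseline/Pre-implant Required prior to Index Procedure", contains KCCQ, EQ-5D and the modified Rankin score, among others. The version 1F entry in the Version History shows that the split was deliberate: "Separated baseline assessments to clarify which are required prior to screening submission and which are required prior to the index procedure".

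The Visit Windows table in the same section gives a single baseline window, "Within 12 weeks prior to submitting to the screening committee (except for MDCT and coronary arteriography", and then refers back to Section 3.3.9. KCCQ is not among its exceptions.

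Under Protocol Section 3.3.8, "Subjects confirmed eligible for implantation by the Screening Committee will be randomized in a 1:1 fashion to either TAVR or SAVR". Step 9 adds: "Trial randomization will not be blinded". Step 10 allows up to 90 days from committee approval to implantation.

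Protocol Section 3.3.3.7 and SAP Section 6.9 set a fixed testing sequence. Item 4 is KCCQ change to 1 year (non-inferiority, margin 5 points, posterior threshold 0.95). Item 7 is KCCQ change to 30 days (superiority, threshold 0.975). Primary-endpoint superiority is tested only after all seven items pass. SAP Section 6.9.1 defines item 7 on raw change: "For subjects with KCCQ score at both baseline and 30 days, the change in KCCQ will be calculated as" the 30-day score minus the baseline score. Item 4 is built the same way. Both use a Bayesian two-sample t-test, with no baseline adjustment stated.

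**The concern.** KCCQ is self-reported. A patient who already knows whether surgery or a catheter procedure is coming may answer differently from one who does not, and the difference may depend on the arm. Randomisation does not balance a value that is measured after assignment is known. Adjusting for baseline would not repair it either, because the covariate would itself have been affected by assignment.

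Two of the seven gates depend on this value. Item 7 is also a labelling claim in its own right, and a failure at item 4 closes items 5 to 7 and the primary superiority test. The KCCQ items are evaluated once. Neither document requires KCCQ before randomisation or plans a sensitivity analysis by the timing of the questionnaire.

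**Working it through.** **Order of events.** Consent, then the first baseline list, committee submission and approval, open-label randomisation, up to 90 days from approval to the procedure, and follow-up. The Visit Windows table would put KCCQ before submission. The specific list lets it fall anywhere before the procedure, including after randomisation. Baseline NYHA (item 3) is on the first list, so the exposed gates are items 4 and 7 only.

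**How a shift passes through.** The estimate is (F_T − B_T) − (F_S − B_S), where F is the follow-up mean, B the baseline mean, and T and S are TAVR and SAVR. If knowledge of the arm moves reported baseline by b_T and b_S, the estimate moves by −(b_T − b_S). Write the net shift favouring TAVR as s = b_S − b_T. If a share q of each arm is assessed late and the arm difference among those subjects is d, then s = q × d.

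**Inputs.** The plan gives no SD, sample size or power for KCCQ, so there is no KCCQ figure to reproduce. The following are assumptions:
- SD of change: 18 to 25 points.
- Subjects with both scores: 400 to 550 per arm. For comparison, the plan's 850 and 1200 subjects are 425 and 600 per arm.
- Priors vague enough for thresholds 0.975 and 0.95 to act like one-sided critical values 1.96 and 1.645.

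**Standard error.** SE = SD × √(2/n).
- Smallest: 18 × √(2/550) = 1.09.
- Largest: 25 × √(2/400) = 1.77.

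**Error rates.** Item 7, true difference zero: P(Z > 1.96 − s/SE). Item 4, true difference −5: P(Z > 1.645 − s/SE).

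| Net shift s | Item 7, SE 1.77 | Item 7, SE 1.09 | Item 4, SE 1.77 | Item 4, SE 1.09 |
|---|---|---|---|---|
| 0 | 0.025 | 0.025 | 0.050 | 0.050 |
| 0.4 | 0.042 | 0.056 | 0.078 | 0.101 |
| 1 | 0.082 | 0.150 | 0.140 | 0.235 |

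The 1-point row for item 7 is P(Z > 1.96 − 0.57) and P(Z > 1.96 − 0.92). For item 4 it is P(Z > 1.645 − 0.57) and P(Z > 1.645 − 0.92).

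**Effect of the late share.** A net shift of 1 point needs a 5-point arm difference if 20% are assessed late (0.20 × 5 = 1). With a 2-point difference among the same 20%, s = 0.4, which is the middle row.

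**Shift against TAVR.** Item 4 power at a true difference of zero is Φ((5 + s)/SE − 1.645). With s = −1 it falls from 0.998 to 0.979 (SE 1.09) or from 0.88 to 0.73 (SE 1.77).

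**The case against.** The strongest reply is that the Visit Windows table already places every baseline KCCQ before committee submission, and therefore before randomisation. If sites followed it, the bias is nil. That stands as a possibility. But the table defers to Section 3.3.9, where the specific list says otherwise, and the version history shows the later timing was intended. The two places conflict; the table does not settle the matter.

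Second, the size is hypothetical. This stands. A reader might infer that baseline scores were in fact collected after assignment, or that the bias favours TAVR. The documents support neither: they permit late completion but do not show how often it occurs or which way any shift would run. The 1-point figures are for a net shift over all subjects, and among a 20% late share that would need an arm difference as large as the plan's own 5-point minimum clinically relevant difference.

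Third, a reader might suppose that an adverse shift costs as much as a favourable one gains. It does not. For 1 point, item 4 power at zero difference falls by about 0.02 (SE 1.09) or 0.15 (SE 1.77), while error at the margin rises by about 0.18 or 0.09 respectively. Item 7's false-positive rate cannot fall by more than 0.025.

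Fourth, a baseline close to treatment is a defensible choice for a change score, since time zero in the as-treated set is the attempted procedure (SAP Section 6.2.2). This is a real cost of moving KCCQ earlier. Finally, follow-up KCCQ is also answered open label, so an earlier baseline removes only the avoidable part of the problem.

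**Conclusion.** The point holds as an avoidable gap in timing and an inconsistency within Protocol Section 3.3.9. A compliant site can take baseline KCCQ after the arm is known, and items 4 and 7 carry any resulting net shift in full. Under the stated assumptions, a net 1 point favouring TAVR takes item 7 from 0.025 to about 0.08 to 0.15 and item 4 at its margin from 0.05 to about 0.14 to 0.23. With a smaller late share the net shift shrinks in proportion. These are stand-alone rates. Item 7 is reached only if items 1 to 6 pass, so its rate within the sequence cannot be higher.

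Confidence is high on the timing and low on the size. It would be wrong to read this as a threat to the main objective: primary non-inferiority does not use KCCQ. What is exposed is the KCCQ claims and access to the later steps, including primary superiority. Open-label follow-up KCCQ remains a separate limitation.

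**What to change.** **Protocol wording.** Reconcile the second baseline list with the Visit Windows table so that KCCQ and, for consistency, EQ-5D are completed after consent and before randomisation. EQ-5D is outside the hierarchy. Leave the timing of the modified Rankin score as it is: nothing here bears on it, and disabling stroke is judged against the pre-stroke score (Protocol Appendix V). The Visit Windows row should therefore name the items that stay on the pre-procedure list.

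**Subjects already randomised.** The Continued Access addendum (Section 3.1) states that it concludes the randomised phase, so the analysis may be the more useful part. Compare each KCCQ date with the randomisation date, report by arm the share completed afterwards, and repeat items 4 and 7 using only baselines completed before randomisation. Add this to SAP Section 6.9 as a sensitivity analysis.

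**Cost.** One wording change and one extra run; no added visit, and no change to sample size, margins or thresholds. A few questionnaires will come from patients who are never randomised. A baseline taken around approval could be about three months old at the procedure (90 days). One taken at the start of the 12-week window could be older (84 + 90 = 174 days, plus committee review), so completion close to randomisation is preferable.
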